3.1 Data analysis general information

The analysis cutoff date for the final analysis of study data will be established when all patients have completed the study. All statistical analyses will be performed using all data collected in the database up to the data cutoff date. All data with an assessment date or event start date (e.g. vital sign assessment date or start date of an adverse event) prior to or on the cutoff date will be included in the analysis. Any data collected beyond the cutoff date will not be included in the analysis and will not be used for any derivations.

All events with start date before or on the cutoff date and end date after the cutoff date will be reported as 'ongoing'. The same rule will be applied to events starting before or on the cutoff date and not having documented end date. This approach applies, in particular, to adverse event and concomitant medication reports. For these events, the end date will not be imputed and therefore will not appear in the listings.

General analysis conventions

Pooling of centers: Unless specified otherwise, data from all study centers will be pooled for the analysis. Due to expected small number of patients enrolled at centers, no center effect will be assessed.

Qualitative data (e.g., gender, race, etc.) will be summarized by means of contingency tables; a missing category will be included as applicable. Percentages will be calculated using the number of patients in the relevant population or subgroup as the denominator.

Quantitative data (e.g., age, body weight, etc.) will be summarized by appropriate descriptive statistics (i.e. mean, standard deviation, median, minimum, and maximum).

3.1.1 General definitions

Investigational drug and study treatment

Investigational drug/study treatment, will refer to the ruxolitinib in this single arm study.

Date of first administration of study treatment

The date of first administration of study treatment is derived as the first date when a nonzero dose of study treatment was administered as per the DAR eCRF. The date of first administration of study treatment will also be referred as *start of investigational drug*.

Date of last administration of study treatment

The date of last administration of study treatment is defined as the last date when a nonzero dose of study treatment was administered as per DAR eCRF. The date of last administration of study treatment will also be referred as *end of investigational drug*.

Study day

The study day, describes the day of the event or assessment date, relative to the reference start date.

The study day is defined as:

- The date of the event (visit date, onset date of an event, assessment date etc.) – reference start date + 1 if event is on or after the reference start date;
- The date of the event (visit date, onset date of an event, assessment date etc.) – reference start date if event precedes the reference start date.

The reference start date for all assessments (e.g. safety, efficacy, PK, [REDACTED], etc.) is the start of study treatment.

The study day will be displayed in the data listings. If an event starts before the reference start date, the study day displayed on the listing will be negative.

Time unit

A year length is defined as 365.25 days. A month length is 30.4375 days (365.25/12). If duration is reported in months, duration in days will be divided by 30.4375. If duration is reported in years, duration in days will be divided by 365.25.

Baseline

For safety and efficacy evaluations, the last available assessment on or before the date of start of study treatment is defined as “baseline” assessment.

If patients have no value as defined above, the baseline result will be missing.

On-treatment assessment/event and observation periods

The overall observation period will be divided into three mutually exclusive segments:

1. ***pre-treatment period***: from day of patient’s informed consent to the day before first administration of ruxolitinib
2. ***on-treatment period***: from date of first administration of study treatment to 30 days after date of last actual administration of ruxolitinib (including start and stop date)
3. ***post-treatment period***: starting at day 31 after last administration of ruxolitinib.

Safety summaries (tables, figures) include only data from the on-treatment period with the exception of baseline data which will also be summarized where appropriate (e.g. change from baseline summaries). In addition, a separate summary for death including on-treatment and post-treatment deaths will be provided. In particular, summary tables for adverse events (AEs) will summarize only on-treatment events, with a start date during the on-treatment period (***treatment-emergent*** AEs).

However, all safety data (including those from the post-treatment period) will be listed and those collected during the pre-treatment and post-treatment period will be flagged.

Windows for multiple assessments

In order to summarize data collected over time (including unscheduled visits), the assessments will be time slotted. The following general rule will be applied in creating the assessment windows: If more than one assessment is done within the same time window, the assessment performed closest to the target date will be used. If two assessments within a time window are equidistant from the target date, then the earlier of the two assessments will be used. If multiple assessments on the same date then the worst case will be used. Data from all assessments (scheduled and unscheduled), including multiple assessments, will be listed.

The following time windows are defined for descriptive summaries on aGvHD assessment, biomarkers and safety ([Table 2-1](#)) by visit. The end of treatment assessment will be mapped into the time points as appropriate.

Table 2-1 Time windows for aGvHD assessment, [REDACTED] and safety assessment (lab, vital sign, growth, etc.)

Time Window	Planned Visit Timing	Time Window Definition
-------------	----------------------	------------------------

On treatment

Baseline (Day 1)	On or before Study Day 1	≤ Study Day 1
Week 1	Study Day 7	Study Days 4 – 10
Week 2	Study Day 14	Study Days 11 – 17
Week 3	Study Day 21	Study Days 18 – 24
Week 4	Study Day 28	Study Days 25 – 31
Week 5	Study Day 35	Study Days 32 – 38
Week 6	Study Day 42	Study Days 39 – 45
Week 7	Study Day 49	Study Days 46 – 52
Week 8	Study Day 56	Study Days 53 – 59
Week 12	Study Day 84	Study Days 71 – 98
Week 16	Study Day 112	Study Days 99 – 126
Week 20	Study Day 140	Study Days 127 – 154
Week 24	Study Day 168	Study Days 155 – 182
Week 28	Study Day 196	Study Days 183 – 210
Week 32	Study Day 224	Study Days 211 – 238
Week 36	Study Day 252	Study Days 239 – 266
Week 40	Study Day 280	Study Days 267 – 294
Week 44	Study Day 308	Study Days 295 – 322
Week 48	Study Day 336	Study Days 323 – 350
Month 12*	Study Day 365	Study Days 351 – 455
Month 18*	Study Day 546	Study Days 456 - 636
Month 24*	Study Day 730	Study Days 637 - 820

Study Day 1 = start date of study treatment;

EOT assessments are mapped to the time points as appropriate;

Last contact date

The last contact date will be derived for patients not known to have died at the analysis cutoff using the last complete date among the following:

Table 3-2 Last contact date data sources

Source data	Conditions
Last contact date/last date patient was known to be alive from Survival Follow-up page	Patient status is reported to be alive, lost to follow-up or unknown.
Start/End dates from new aGVHD treatment since discontinuation from study treatment	Non-missing medication/procedure term.
Start/End dates from drug administration/concomitant medication record	Non-missing dose. Doses of 0 are allowed.
Disposition event date from the disposition log page	No condition.

Source data	Conditions
- aGvHD assessment date - any specific efficacy assessment date if available (e.g., cGvHD assessment, graft failure assessment, second primary malignancy assessment, hematologic disease relapse/progression assessment)	Non-missing assessment
Laboratory/PK collection dates/ [REDACTED] [REDACTED]	Sample collection marked as 'done'.
Vital signs date	At least one non-missing parameter value
Collection date of acceptability and palatability questionnaire	Assessment performed is "Yes" [REDACTED]
Start/End dates of AE	Non-missing verbatim term

The last contact date is defined as the latest complete date from the above list on or before the data cutoff date. The cutoff date will not be used for last contact date, unless the patient was seen or contacted on that date. No date post cutoff date will be used. Completely imputed dates (e.g. the analysis cut-off date programmatically imputed to replace the missing end date of a dose administration record) will not be used to derive the last contact date. Partial date imputation is allowed for event (death)/censoring coming from 'Survival information' eCRF.

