9.1.3 Lost to follow-up

For patients whose status is unclear because they fail to appear for study visits without stating an intention to discontinue from study treatment or discontinue from study or withdraw consent/oppose to the use of their data/biological samples, the investigator should show "due diligence" by contacting the patient, family or family physician as agreed in the informed consent and by documenting in the source documents steps taken to contact the patient, e.g. dates of telephone calls, registered letters, etc.

A patient should not be considered lost to follow-up until due diligence has been completed. Patients lost to follow up should be recorded as such on the appropriate Disposition CRF.

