3.7 Analysis of secondary efficacy objective(s)

3.7.1 Secondary endpoints

- **Overall Response Rate at Day 14**

Overall Response Rate at Day 14 is defined as the proportion of patients with complete response (CR) or partial response (PR) at Day 14 according to standard criteria [\[Harris 2016\]](#).

- **Duration of response (DOR)**

Duration of response will be calculated for patients whose overall response at Day 28 is CR or PR according to updated standard criteria [\(Harris et al 2016\)](#). The start date is the date of first documented response of CR or PR (i.e., the start date of response), which could be prior to or at Day 28. If it's prior to Day 28, there should not be progression or addition of systemic therapies for aGvHD between the start date of response and Day 28. The end date is defined as the date of progression or the date of addition of systemic therapies for aGvHD on or after Day 28, since this constitutes a non-response. The date of progression will be the earliest date of PD recorded in the aGvHD assessment CRF page or the date of death due to aGvHD in the death CRF page.

Death without prior observation of aGvHD progression (i.e. date of death due to non aGVHD reason (Other) in the death CRF page) and onset of chronic GvHD are considered to be competing risks.

Duration of response will be censored at the last response assessment prior to or at the analysis cut-off date, if no events/competing risk occurred before or at of cut-off date.

- **Best Overall Response**

Best overall response (BOR) is defined as proportion of patients who achieved overall response (CR or PR) at any time point up to and including Day 28 and before the start of additional systemic therapy for aGvHD.

An additional analysis will include BOR at any time point up to the data cut-off date and before the start of additional systemic therapy for aGvHD. A swimmer plot for overall response by age group, SR-aGvHD vs Treatment Naive and formulation will also be provided for all treated subjects.

- **Overall survival (OS)**

Overall survival is defined as the time from date of the start of study treatment to date of death due to any cause. If a patient is not known to have died, then OS will be censored at the latest date the patient was known to be alive (last contact date on or before the cut-off date).

- **Event Free Survival (EFS)**

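### The last-contact rule accepts the disposition date unconditionally, so follow-up of a child declared lost can be censored after the last date the child was known to be alive

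*SAP*

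**What the plan says.** SAP section 3.1.1 derives a last contact date for every patient not known to have died. Table 3-2 names the sources, each with a condition for use. The Survival Follow-up page, which supplies the last date the patient was known to be alive, is used under this condition: "Patient status is reported to be alive, lost to follow-up or unknown". The assessment, laboratory, vital-sign, dosing and adverse-event rows each need a real entry. The row "Disposition event date from the disposition log page" is the only one stated to need no condition.

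The selection rule is: "The last contact date is defined as the latest complete date from the above list on or before the data cutoff date". The same paragraph limits two other kinds of date. Completely imputed dates are barred, and for the cutoff: "The cutoff date will not be used for last contact date, unless the patient was seen or contacted on that date".

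The date feeds censoring in SAP section 3.7.1. For overall survival, "then OS will be censored at the latest date the patient was known to be alive". EFS, FFS, NRM, malignancy relapse/progression and cGvHD follow the same rule. Duration of response does not; it is censored at the last response assessment.

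Protocol 9.1.3 governs loss to follow-up: "A patient should not be considered lost to follow-up until due diligence has been completed", and then "Patients lost to follow up should be recorded as such on the appropriate Disposition CRF".

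**The concern.** A declaration of loss is not evidence that the child is alive. Where it is dated later than the last visit, call or assessment, the latest-date rule lets it override the Survival Follow-up page, the source meant to hold the last-known-alive date. The SAP applies a seen-or-contacted test to the cutoff date but not to this row.

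The lost child then stays in the risk set, event-free, through a period in which nobody observed the child. Larger risk sets make each death count for less, so the Kaplan-Meier curves can only rise or stay the same. Cumulative incidences generally fall; with competing risks a single component need not fall in every data set. The trial has one arm, so no comparator shares the shift.

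**Working it through.** **Step 1. The design figure.** The only related probability in the plan is for the primary endpoint: 0.901 that the 90% CI for Day 28 ORR has a lower limit of at least 60% (n = 45, true ORR 80%). It reproduces: P(X ≥ 33 | 45, 0.8) = 0.9005, and the Clopper-Pearson lower limit for 33/45 is 0.604. It does not use the last contact date. The plan gives no figure for loss to follow-up.

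**Step 2. How the shift arises.** Suppose one death occurs between a lost child's last contact and the disposition date, with 20 other children at risk (an illustrative number). Censoring at last contact multiplies the curve by 1 − 1/20 = 0.950. Censoring at the disposition date multiplies it by 1 − 1/21 = 0.952.

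**Step 3. Inputs for size.**
- n = 45 and 24 months of follow-up (protocol).
- 24-month OS of 22%: from the adult study's ruxolitinib median of 11.1 months (Protocol 1.1.2.1.2), 0.5^(24/11.1) = 0.223.
- 24-month OS of 30%: upper end of the 20–30% two-year range in Protocol 1.1.1.
- 24-month OS of 65%: assumed, as a more favourable case.
- Children lost: 1, 2, 5 or 9 of 45, at a uniform time between months 1 and 18 (assumed).
- Delay from last contact to disposition date: 1, 3 or 6 months (assumed; long-term visits are six months apart, Protocol 9.1.5).
- Exponential survival and non-informative loss (assumed).

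**Step 4. Result.** Kaplan-Meier simulation, 1,500 trials per cell. The entry is the 24-month estimate with censoring at the disposition date minus the estimate with censoring at last contact, in percentage points. Ranges span the three survival levels.

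| Children lost | Delay 1 month | Delay 3 months | Delay 6 months |
|---|---|---|---|
| 1 | 0.03 | 0.08–0.11 | 0.16–0.23 |
| 2 | 0.06–0.07 | 0.15–0.21 | 0.33–0.47 |
| 5 | 0.13–0.18 | 0.42–0.56 | 0.84–1.21 |
| 9 | 0.27–0.34 | 0.78–1.07 | 1.58–2.29 |

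Mean follow-up lengthens by about 0.01 to 1.0 month. With no delay, the shift is zero.

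A second simulation placed losses on the protocol visit schedule, with disposition logged 1 to 3 months after the first missed visit, 24-month OS of 55% and a front-loaded Weibull hazard (shape 0.6). It gave 0.3–0.4 points with 5% lost, 0.7–0.9 with 10% and 1.4–1.9 with 20%.

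**Step 5. Scale.** The approximate 95% half-width is 1.96 × √(S(1 − S)/45): 12.2 points at S = 0.223, 13.4 at 0.30 and 13.9 at 0.65. The largest shift is 2.29/13.4 = 17% of the half-width. With two children lost and a six-month delay it is 0.47/13.4 = 3.5%.

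**The case against.** The strongest objection is that the decisive fact is not in the documents. Protocol 9.1.3 says when a child may be declared lost and on which form, but not which date goes in the field. If sites enter the last contact date, the rule does no harm. This stands. A reader might infer that lost children are in fact carried as alive to an administrative date; the documents make that plausible but do not establish it.

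A reader might also extend the point to early termination by the sponsor. Protocol 9.1.4 requires each patient to be seen as soon as possible in that case, with discontinuation assessments, so a real contact is planned. That extension is not supported.

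The delay is also uncertain. Table 8-1 schedules Disposition only at end of treatment, where visits are weekly and then every four weeks. In long-term follow-up the scheduled status source is the Survival Follow-up page. A six-month delay therefore needs an unscheduled disposition entry after end of treatment. Protocol 9.1.3 leaves room for one, but does not show that it will happen. The attempts to reach the family or family physician may also uncover a death, which takes that child out of this derivation.

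Finally, the affected endpoints are descriptive secondary estimates, and no efficacy hypothesis is tested. This limits the importance of the point. It does not justify a row that escapes the test applied to the cutoff date in the same paragraph.

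**Conclusion.** The point holds as a flaw in a stated rule whose effect is conditional. As written, Table 3-2 allows the censoring date for six endpoints to fall after the last date a child was known to be alive, contrary to the SAP's own wording for those endpoints. The undefined field also means that the meaning of the censoring date depends on what each site enters.

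The effect is zero if the disposition field holds the last contact date. If it holds a later declaration date, survival moves in the favourable direction, by about 0.03 to 2.3 points at 24 months for 1 to 9 of 45 children lost and delays of 1 to 6 months. Those rates and delays are assumptions. Only OS was simulated, and loss related to prognosis was not modelled. The shift is small against the confidence interval. Day 28 ORR, durable Day 56 ORR and duration of response do not change.

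**What to change.** In SAP Table 3-2, replace the absence of a condition on the disposition row with a requirement that the patient was seen or contacted on that date. Where the disposition reason is loss to follow-up, use the last-known-alive date from the Survival Follow-up page or, if later, the last actual assessment. It would also help to state which date sites enter on the disposition page for a lost child.

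The cost is one extra condition in the derivation program and possibly slightly less favourable survival estimates. If the page already records last contact, the results do not change and the safeguard is documented. The change belongs before final database lock, the point by which the SAP says its analysis decisions are made.

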3.2 Analysis sets

If the starting dose is different from the assigned dose level due to co-administration of ruxolitinib with strong CYP3A4 or dual CYP3A4/CYP2C9 inhibitors, these patients will be included under the assigned dose level and considered that they have received the full assigned dose. This applies to all analysis sets described below.

The **Full Analysis Set** (FAS) comprises all patients to whom study treatment has been assigned and who received at least one dose of study treatment. Patients will be analyzed according to the treatment they have been assigned to.

The **Safety Set** includes all patients who received at least one dose of study treatment. Patients will be analyzed according to the study treatment received, where treatment received is defined as the assigned dose level of ruxolitinib if the patient took at least one dose of that treatment or the first dose level received if the assigned dose level was never received.

The **Pharmacokinetic Analysis Set** (PAS) includes all patients who provide at least one evaluable PK concentration. For a concentration to be evaluable, patients are required to:

- Take the dose of ruxolitinib prior to PK sample.
- For pre-dose samples, do not vomit within 2 hours after the previous dosing of ruxolitinib prior to sampling; for post-dose samples, do not vomit within 2 hours after the dosing of ruxolitinib.

The PAS will be used for Non-compartmental analysis (NCA) for patients where extensive PK sampling is obtained. This analysis set will also be used for any exposure-response analysis

The **Efficacy Eevaluable Set** (EES) comprises all patients to whom study treatment has been assigned at the Recommended Phase 2 dose (RP2D) of ruxolitinib and who received at least one dose of study treatment at that dose level. If the starting dose is different from the RP2D due to co-administration of ruxolitinib with strong CYP3A4 or dual CYP3A4/CYP2C9 inhibitors, these patients will be included in the EES.

All statistical analysis and data presentation for all analysis sets will exclude any data collected but not required as per study protocol. Data with a Protocol Deviation Code OTH11 (Other GCP deviation- Additional samples or Data collected not required as per protocol) will not be part of the analysis data or any output presentation.

Any patients who withdrew Informed Consent or from whom written Informed Consent was not obtained (Protocol Deviation INCL01) will be excluded from all analyses sets.

Any data collected in the clinical database (other than acute GvHD biopsy, medical history, prior and concomitant medication, donor information, prior or concomitant non-drug therapies/procedures and viral load, serology from lab data, [REDACTED] and blood component transfusion) before signed of informed consent will not be included in the analysis. If a patient withdraws informed consent from all further participation in the trial no data will be included in the analysis after withdrawal of informed consent date. The informed consent date and the date on which a patient withdraws full consent are recorded in the eCRF.

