6.2.1.2 Permitted concomitant therapy requiring caution and/or action

Patients receiving ruxolitinib with concomitant medications provided per standard institutional guidelines for management after alloSCT including: anti-emetics, CNIs, azole fungal prophylaxis, broad spectrum antibiotics in the event of fever (either semi-synthetic penicillin or third generation cephalosporin with vancomycin, gentamicin or equivalent), acyclovir prophylaxis, ganciclovir, foscarnate, G-CSF, steroid pre-meds prior to RBC/platelet transfusions, narcotics, and sedatives warrant close monitoring of potential drug-drug interaction effects of these concurrent drugs.

Ruxolitinib dose adjustments may be required, particularly in patients treated with CYP450 modulators (See [Section 6.5.2](#)).

Upon initiation of a strong CYP3A4 inhibitor or a dual CYP3A4/CYP2C9 inhibitor, including fluconazole up to a dose of 6 mg/kg (maximum 200 mg) daily, the dose of ruxolitinib may be reduced (e.g. by 50%), and more frequent monitoring of hematology parameters and clinical signs and symptoms of ruxolitinib related adverse events is recommended. The patient and the Investigator should be aware of potential signs of overdose of the concomitant medications and in the event of suspected study drug related toxicity, administration of ruxolitinib should be dose reduced or held according to guidelines (See [Table 6-3](#)) and Investigator judgment, with appropriate corticosteroid immunosuppression provided to avoid aGvHD flare.

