12.1 Analysis sets

If the starting dose is different from the assigned dose level due to co-administration of ruxolitinib with strong CYP3A4 inhibitors or dual CYP3A4/CYP2C9 inhibitors, these patients will be included under the assigned dose level and considered that they have received the full assigned dose. This applies to Full Analysis Set, Safety Set and Efficacy Evaluable Set as described below.

The **Full Analysis Set (FAS)** comprises all patients to whom study treatment has been assigned and who received at least one dose of study treatment. Patients will be analyzed according to the treatment they have been assigned to.

The **Safety Set** includes all patients who received at least one dose of study treatment. Patients will be analyzed according to the study treatment received, where treatment received is defined as the assigned dose level of ruxolitinib if the patient took at least one dose of that treatment or the first dose level received if the assigned dose level was never received.

The **Pharmacokinetic Analysis Set (PAS)** includes all patients who provide at least one evaluable PK concentration. For a concentration to be evaluable, patients are required to:

1. Take the dose of ruxolitinib prior to PK sample.
2. For pre-dose samples, do not vomit within 2 hours after the dosing of ruxolitinib prior to sampling; for post-dose samples, do not vomit within 2 hours after the dosing of ruxolitinib.

The PAS will be used for Non-compartmental analysis (NCA) for patients where extensive PK sampling is obtained. This analysis set will also be used for any exposure-response analysis

The **Efficacy Evaluable Set** (EES) comprises all patients to whom study treatment has been assigned at the Recommended Phase 2 dose (RP2D) of ruxolitinib and who received at least one dose of study treatment at that dose level. If the starting dose is different from the RP2D due to co-administration of ruxolitinib with strong CYP3A4 inhibitors or dual CYP3A4/CYP2C9 inhibitors, these patients will be included in the EES.

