3.9 Pharmacokinetic endpoints

Pharmacokinetic Analysis Set (PAS) will be used in all pharmacokinetic data analysis and PK summary statistics.

In patients with extensive PK sampling on Day 1 (samples 1 to 8 described in [Section 8.6.1.1 of the protocol](#)), PK parameters of ruxolitinib will be calculated by non-compartmental methods using Phoenix WinNonlin (Pharsight, Mountain View, CA) software. The following parameters will be calculated ([Table 2-5](#)). Additional PK parameters may be estimated as needed.

Table 3-5 Non-compartmental pharmacokinetic parameters of ruxolitinib

AUClast	The AUC from time zero to the last measurable concentration sampling time (Tlast)
AUCinf	The AUC from time zero extrapolated to infinity
AUC0-12	The AUC from time zero extrapolated to 12 hours
Cmax	The maximum (peak) observed plasma drug concentration
Ctrough	The minimum observed plasma concentration at the end of an administration interval (corresponding to the pre-dose concentration prior to the following administration)
Tmax	The time to reach maximum (peak) plasma, blood, serum, or other body fluid drug concentration after single dose administration (time)
T1/2	The elimination half-life associated with the terminal slope (Lambda_z) of a semi logarithmic concentration-time curve
CL/F	The total body clearance of drug from the plasma
Vz/F	The apparent volume of distribution during terminal phase (associated with Lambda_z)

All plasma concentrations will be analyzed using a population PK approach.

Statistical methods for pharmacokinetic analyses

All individual plasma ruxolitinib concentrations data will be listed by group. Descriptive summary statistics will be provided by group at each scheduled time point. Summary statistics will include n (number of patients with non-missing values), mean (arithmetic and geometric), SD, CV (arithmetic and geometric), median, minimum and maximum. Individual profiles with median by dose level as well as arithmetic mean with SD and geometric mean ruxolitinib plasma concentration versus time profiles by treatment will be displayed graphically.

Ruxolitinib plasma PK parameters data will be listed by group. Descriptive statistics (n, arithmetic mean, standard deviation (SD), coefficient of variation (CV)% for mean, geometric mean, geometric CV%, median, minimum and maximum) will be provided for all PK parameters by dose level except for Tmax where median, minimum and maximum will be presented.

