Sample size	Minimum No. of responders	Response Rate	Probability to have a 90% CI with lower limit $\geq 60\%$	90% CI	
37	28	0.76	0.809	0.614	0.867
38	29	0.76	0.784	0.623	0.871
39	29	0.74	0.859	0.604	0.854
40	30	0.75	0.839	0.613	0.858
41	31	0.76	0.818	0.621	0.861
42	31	0.74	0.882	0.604	0.846
43	32	0.74	0.864	0.612	0.849
44	33	0.75	0.846	0.620	0.853
45	33	0.73	0.901	0.604	0.838
46	34	0.74	0.886	0.612	0.842
47	35	0.74	0.869	0.619	0.846
48	35	0.73	0.916	0.604	0.832
49	36	0.73	0.903	0.612	0.835
50	37	0.74	0.889	0.619	0.838

5 Change to protocol specified analyses

No change from protocol

6 Appendix

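### SAP 3.2 extends the full-assigned-dose rule for CYP inhibitor patients to the PK analysis set, which protocol 12.1 does not, and SAP section 5 declares no change

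*SAP*

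**What the plan says.** Both documents open their analysis-set section with the same rule for patients whose starting dose differs from the assigned level because of a strong CYP3A4 or dual CYP3A4/CYP2C9 inhibitor. In the SAP's words, "these patients will be included under the assigned dose level and considered that they have received the full assigned dose". The documents differ on where the rule applies:

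- Protocol 12.1: "This applies to Full Analysis Set, Safety Set and Efficacy Evaluable Set as described below". The PAS is defined in the same section but is not named.
- SAP 3.2: "This applies to all analysis sets described below". The PAS is one of the sets that follow.
- SAP section 5, on changes to protocol-specified analyses: "No change from protocol".

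Membership of the PAS does not depend on dose or inhibitor use. The set "includes all patients who provide at least one evaluable PK concentration". On its use: "The PAS will be used for Non-compartmental analysis (NCA) for patients where extensive PK sampling is obtained". SAP 3.9 lists AUClast, AUCinf, AUC0-12, Cmax, Ctrough, Tmax, T1/2, CL/F and Vz/F, and gives full descriptive statistics for all "PK parameters by dose level except for Tmax". SAP 3.5.2 compares PK parameters with adults by geometric mean ratio (GMR) and 90% CI.

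**The concern.** The rule makes sense for classification. A patient whose dose was lowered to offset an inhibitor can reasonably count at the assigned level for efficacy and safety. In a PK set, the administered dose is a property of the profile and an input to some parameters.

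The rule concerns the starting dose, and the NCA uses the Day 1 samples, so it bears directly on the profiles behind the Phase I primary endpoint. Such patients are plausible: protocol 6.2.1.2 lists azole prophylaxis among usual concomitant care, and Appendix 6 classes several azoles as strong or dual inhibitors. Groups 2 and 3 plan five evaluable profiles each, so one patient is a fifth of a group.

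Two things are at stake. A table labelled with one dose level may hold profiles from a lower dose taken with an inhibitor, unmarked. And the only rule in the SAP on which dose counts for these PAS patients points to a dose they did not take.

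**Working it through.** **1. The plan's own PK precision figure.** Protocol 12.8.1 and SAP section 4 give a CI of 0.609 to 1.641 for a Cmax GMR of 1, with 5 pediatric patients (CV 55.7%) and about 25 adults (CV 40%).

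- Log-scale variance is ln(1 + CV²): ln(1 + 0.557²) = 0.2702 and ln(1 + 0.40²) = 0.1484.
- SE = √(0.2702/5 + 0.1484/25) = 0.2449.
- Welch–Satterthwaite df = 4.92, so t(0.95) = 2.0226.
- CI = exp(±2.0226 × 0.2449) = 0.609 to 1.641.

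The figure reproduces as a two-sided 90% Welch interval. The dose rule does not enter it.

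**2. Which listed parameters depend on dose.** CL/F and Vz/F are proportional to the dose entered. AUC, Cmax, Ctrough, Tmax and T1/2 come from concentrations and times alone. Neither document plans a dose-normalised AUC or Cmax.

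**3. CL/F and Vz/F if the deemed dose were used.** Assume k of 5 patients took 50% of the assigned dose. The 50% is the protocol's example in 6.2.1.2, where the reduction is optional. Each affected value is doubled relative to the value on the administered dose, so the group geometric mean is multiplied by 2^(k/5):

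| k of 5 | CL/F, Vz/F | Observed AUC, Cmax |
|---|---|---|
| 0 | 1.00 | 1.00 |
| 1 | 1.15 | 1.00 |
| 2 | 1.32 | 1.00 |
| 3 | 1.52 | 1.00 |
| 4 | 1.74 | 1.00 |
| 5 | 2.00 | 1.00 |

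**4. Summaries by dose level.** Under the SAP sentence, a half-dose profile with an inhibitor is tabulated at the full level. The effect on the tabulated means cannot be computed, because the documents do not give the net exposure of a reduced dose with an inhibitor in these children.

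**5. Precision without inhibitor patients.** Repeating step 1 at GMR = 1 with fewer pediatric profiles gives 0.549 to 1.822 for four and 0.434 to 2.305 for three. The latter passes the plan's 2-fold limit.

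**The case against.** The strongest reply is that the sentence sits under analysis sets and reads as classification. It says where a patient is counted, and no text tells the NCA to enter the assigned dose. The SAP's own practice supports this: the rule also covers the Safety Set, yet SAP 3.4.1 computes dose intensity there from the actual dose on the study treatment eCRF. A pharmacokineticist would probably use the administered dose. This stands, so the inflation of CL/F and Vz/F is conditional. It does not remove the conflict in scope or the mixing by dose level, which follows from the classification reading itself.

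A reader might infer more, and the documents do not support it:

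- *That the RP2D decision is biased.* Protocol 3.1.1 and SAP 2.1.1 rest confirmation on AUC and Cmax, which a label leaves unchanged.
- *That dose-normalised PK is distorted.* No dose-normalised AUC or Cmax is planned; only CL/F and Vz/F use dose.
- *That exposure-response is affected.* The models in SAP 3.10 use trough concentrations, and population PK exposures are to account for dose modifications.
- *That the protocol wording would take inhibitor patients out of the adult comparison.* They remain in the PAS under both texts.

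It is also fair that the number of affected patients is unknown and may be zero, and that a 15% shift is small beside an interval of 0.609 to 1.641. Doses, concentrations and inhibitor use are all reported, but in separate outputs. The sections available to read plan no inhibitor flag in the PK outputs.

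**Conclusion.** The conflict is real, is in the current text of both documents, and is undeclared, although SAP amendment 3 was meant to align with protocol amendment 3. Its certain consequence is limited: any reduced-dose profile taken with an inhibitor is grouped with full-dose profiles in the PK summaries by dose level. Its conditional consequence is an overstatement of geometric mean CL/F and Vz/F by about 15% for one patient in five and 32% for two. That rests on a 50% reduction, on such patients being among the five, and on the deemed dose being entered in the NCA. AUC, Cmax, their GMR and the planned interval are unaffected.

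Protocol amendment 3 reports enrolment complete, so what remains at risk is the final PK reporting. The text should be corrected before those outputs are produced, but it does not threaten the dose confirmation or the efficacy analysis.

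**What to change.** - Limit the SAP 3.2 sentence to the Full Analysis Set, Safety Set and Efficacy Evaluable Set, as in protocol 12.1.
- State that, for the PAS, CL/F and Vz/F use the administered dose and PK summaries are by actual dose. The protocol does not say this either, so restoring its scope is not enough.
- Flag profiles taken with a strong or dual inhibitor in the PK listings.
- Show the PK summaries and the adult GMR with and without those profiles. This is an added sensitivity analysis, not a return to protocol text.

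The administered doses are already recorded on the dosing eCRF, so no new data are needed. The cost is a few sentences and a few more outputs. The version without inhibitor patients has fewer profiles and wider intervals, as shown in the last step of the working, so it should be read as descriptive.
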